14. DATA MANAGEMENT

14.1 Confidentiality

Confidentiality of subject data will be maintained at all times. Subject confidentiality will be maintained throughout the clinical study in a way that ensures the information can always be tracked back to the source data. Subject anonymity will be guaranteed and all documentation relating to a subject will be kept in a secure location.

14.2 Subject Identification (ID)

A unique Subject Identifier (ID) will identify enrolled patients, which is a combination of a non-repeating, sequential number starting with P01, followed by the site ID. The site ID for UVN is S01 and the site ID for Beaumont Hospital is S02. In the advent of new sites being added, additional site numbers will be assigned sequentially.

14.3 Data Collection

The Paper based Case Report Form (CRF) is the primary data collection instrument for this study. Prior to the start of the clinical investigation, Sponsor will provide the Case Report Forms (CRF) for each individual subject. The recording of data on the visit specific Case Report Forms will be completed in full by Investigator/Study Coordinator for each individual subject. The sponsor or its designee will promptly address any data issues with the Investigator. All missing data must be explained. If a space on the CRF is left blank because the procedure was not done or the question was not asked, write "N/D". If the item is not applicable to the individual case, write "N/A". All entries should be printed legibly in black or blue ink. If any entry error has been made, to correct such an error, draw a single straight line through the incorrect entry and enter the correct data, above it. All such changes must be initialed and dated by the individual making the correction. DO NOT ERASE OR WHITE OUT ERRORS.

The personal data recorded on all documents will be regarded as confidential.

Note: The site must record the subject's participation in this clinical investigation in the subject's medical records.

14.4 Review and Return of Completed Study Data

The investigator will maintain all source documents as required by the CIP, including laboratory results, supporting medical records, and signed Informed Consent forms. Sponsor and/or monitor will use source documents during the regular monitoring visits to verify data entered in the CRF. All CRFs will be reviewed for accuracy and the Principal Investigator will sign and date each completed CRF to document approval.

A copy of fully completed original CRFs will be made available to Sponsor.

Once all the subject data has been collected and verified, the analysis and reporting will be conducted. Any data existing for subjects who have not received treatment with PEPNS System will not be used in the analysis. Details of these subjects will, however, are referenced in the final report.

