6.3 Enrollment

Subjects will be screened to determine eligibility i.e., who meet all inclusion and exclusion criteria. Those subjects that meet the eligibility criteria and who agree to participate in the study will sign an Informed Consent form. Subject is deemed to be enrolled into study when the subject provides written informed consent and agrees to participate in the clinical investigation.

All patients that were attempted to be treated with the PEPNS System (i.e., intent-to-treat patients) but the procedure was aborted will also be followed for 30 days (+7 days) post index procedure for safety (i.e., adverse event collection).

A screening log will be used to determine why patients were screened out of the study.

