11.6.2 Withdrawal for Other Reasons OR Non-Treatment

If the patient has signed the ICF but was later found to not meet inclusion/exclusion criteria prior to enrollment or deemed not suitable for treatment by the physician the patient will not be considered enrolled in the study.

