2. ANALYSIS OBJECTIVES

The company informed the FDA of plans to conduct a First in Human feasibility study within an OUS Tier I country (Canada, Europe or Australia) and stated:

As part of this study the following would be evaluated

- a) Confirmation of the stimulation leads are easily deployed under ultrasound guidance
- b) Confirmation that the diaphragm is easily stimulated without collateral stimulation similar to the Taira publication in references.
- c) Confirmation of appropriate candidates for a pivotal study. Trending demonstrating that time to extubation is decreased when compared to historical data in similar patient population.

The first two patients enrolled in the trial will be analyzed specifically for safety of the procedure in terms of nerve damage which could result from electrical stimulation or mechanical damage due to lead insertion, patient movement or lead removal and any other adverse events. Compound motor action potential and nerve conduction time between the neck and diaphragm will be evaluated in the first two pilot patients. Since these patients are stimulated on the left phrenic nerve only, they will be included for the safety analysis only. The enrollment of subsequent patients was contingent upon these patients showing no damage to the phrenic nerve at ~30 days post stimulation in terms of the CMAP study, follow up x-ray and any reported adverse events deemed relevant to the procedure.

Primary and secondary endpoints for the study will be evaluated statistically in terms of per protocol (PP) and intent-to-treat (ITT) analysis. The clinical study protocol CIP0001 defined intent-to-treat as "All patients that were attempted to be treated with the PEPNS System but the procedure was aborted." The

	PEPNS Study Statistical Analysis Plan <small>CONFIDENTIAL: THIS DOCUMENT AND ALL INFORMATION CONTAINED HEREIN IS PROPRIETARY TO STIMDIA MEDICAL, INC. AND IS NOT TO BE DISCLOSED WITHOUT THE EXPRESS WRITTEN PERMISSION OF STIMDIA MEDICAL, INC.</small>	Document Number SAP0001	Rev. Level 1
---	--	-----------------------------------	------------------------

primary analysis will be per protocol and the secondary analysis will be intent-to-treat. Time of weaning from mechanical ventilation and diaphragm thickness from 0 to 48 hours will also be analyzed.

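### No planned analysis clearly includes every attempted lead insertion, so aborted placements and their serious events can be left out of both safety percentages

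*Protocol*

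**What the plan says.** **Enrolment and follow-up.** Protocol 6.3 fixes enrolment at consent: "Subject is deemed to be enrolled into study when the subject provides written informed consent". The same section says of patients in whom treatment was attempted but stopped that they "will also be followed for 30 days (+7 days) post index procedure for safety (i.e., adverse event collection". It attaches the intent-to-treat label to those attempted.

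**Exclusion from analysis.** Protocol 14.4: "Any data existing for subjects who have not received treatment with PEPNS System will not be used in the analysis". The next sentence reads: "Details of these subjects will, however, are referenced in the final report". Neither document defines receipt of treatment.

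**Un-enrolment.** Protocol 11.6.2 concerns a patient who has signed consent but is "later found to not meet inclusion/exclusion criteria prior to enrollment" or is "deemed not suitable for treatment by the physician the patient will not be considered enrolled in the study".

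**Analysis populations.** SAP section 2: "Primary and secondary endpoints for the study will be evaluated statistically in terms of per protocol (PP) and intent-to-treat (ITT) analysis". Sections 2 and 3 make per protocol primary and intent-to-treat secondary. Section 2 takes its intent-to-treat definition from the protocol, as the patients in whom treatment was attempted and the procedure aborted. Section 5 has the per-protocol analysis take in every patient and all their data, so far as applicable.

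**Endpoints.** Two of the three secondary endpoints (Protocol 5.2 and 6.9; SAP section 2) are the percentage with safe and successful lead placement and the percentage with at least one serious device- or procedure-related adverse event. Neither document states a denominator for either.

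**The concern.** Both percentages are meant to show how insertion goes. If a patient leaves the analysis because insertion failed or caused harm, exclusion depends on the outcome being measured, and the bias runs in the favourable direction: placement success moves towards 100% and serious events towards 0%.

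Protocol 6.9 plans no hypothesis test for these endpoints, so the percentage itself is the result that a reader of this first-in-human study will carry forward. With conflicting text the denominator can also be settled after the results are known. The SAP already lists patient identifiers and describes the cohort in the past tense.

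**Working it through.** The plan states no figure on this point, so there is none to reproduce. The check is to follow one patient through the text and then size the effect with assumed counts.

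**Step 1. One patient through the text.** A consented, eligible patient has lead insertion started. The operator stops because of bleeding or a pneumothorax, both risks listed in Protocol 13.1. No stimulation is given.

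- *Protocol 6.3:* the patient is enrolled, and adverse events are collected for 30 to 37 days.
- *Protocol 14.4:* the answer depends on what counts as treatment. Inclusion criterion 4 in 6.2 uses the word for the stimulation period of up to 48 hours, and 6.3 describes aborted patients only as ones whom the team tried to treat. On that usage the patient is untreated and the data are barred. The heading of section 7, on the other hand, calls the whole procedure the treatment procedure. On that usage the data stay in.
- *SAP per protocol (primary):* there is no rule for aborted cases. The breadth of section 5 is qualified by applicability and is not reconciled with 14.4.
- *SAP intent-to-treat (secondary):* the patient is included, but read literally so are only patients like this one. In 6.3 the label sits beside the attempt, before the words about abortion. The SAP definition drops that placement and runs the two together.
- *Protocol 11.6.2:* the eligibility limb carries a timing, the suitability limb carries none, and both conflict with enrolment at consent in 6.3.

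None of these clearly yields a rate over all attempts.

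**Step 2. Size.** Let *s* be patients stimulated and *a* patients aborted. Assume that every stimulated patient had a successful placement and no serious event, and that every aborted patient had a serious procedure-related event. Then:

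- stimulated only: placement *s/s*, serious events 0/*s*
- all attempts: placement *s/(s+a)*, serious events *a/(s+a)*
- literal SAP intent-to-treat: placement 0/*a*, serious events *a/a*

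With *s* = 10 and *a* = 1 (assumed):

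| Denominator | Placement success | Serious events |
|---|---|---|
| Stimulated only | 10/10 = 100% | 0/10 = 0% |
| All attempts | 10/11 = 90.9% | 1/11 = 9.1% |
| Aborted only | 0/1 = 0% | 1/1 = 100% |

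With *a* = 2, all attempts gives 10/12 = 83.3% and 2/12 = 16.7%.

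**Step 3. Range at the enrolment cap.** Protocol 6 allows at most 20 subjects. Take 20 attempts, of which 1, 2 or 3 are aborted (assumed):

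| Aborted | Placement, all attempts | Serious events, all attempts (exact 95% CI) | Serious events, stimulated only (exact 95% upper limit) |
|---|---|---|---|
| 1 | 19/20 = 95% | 5% (0.1 to 24.9) | 0% (17.6) |
| 2 | 18/20 = 90% | 10% (1.2 to 31.7) | 0% (18.5) |
| 3 | 17/20 = 85% | 15% (3.2 to 37.9) | 0% (19.5) |

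Placement among stimulated patients is 100% in every row. Each aborted case moves a percentage by 1/20 = 5 points here, and by 1/12 = 8.3 points with 12 attempts.

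**The case against.** A reader might infer that the plan definitely removes aborted placements from both percentages and hides the injuries they cause. The documents do not support that.

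- The SAP applies an intent-to-treat analysis to the secondary endpoints and defines it by the aborted attempts. SAP section 5 speaks of all patients, and Protocol 6.8 bases analysis on those enrolled.
- Treatment can be read to include insertion. Besides the section 7 heading, the table in Protocol section 2 gives percutaneous lead placement as the study type.
- Protocol 11.6.2 most naturally covers decisions before the procedure. Section 11.2 starts the procedure only after consent and confirmed eligibility, and aborted attempts have their own rule in 6.3.
- Injuries are not hidden from oversight. Protocol 13.6.1 requires all adverse events to be reported, 13.5 provides committee review, 13.6.2 requires serious events to go to the regulators, and 14.4 keeps untreated subjects in the final report.

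Most of this stands. It reduces a certain loss to a possible one and confines it to two descriptive percentages. It does not remove the problem. Follow-up and reporting rules govern collection and notification, whereas 14.4 governs analysis. A mention in the report is neither a numerator nor a denominator. The intent-to-treat analysis is only secondary, and its literal content is a rate among aborted patients alone.

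Two further inferences also lack support. Nothing in the documents says that failures would cluster by operator or site. Nor does SAP Table 3 show that any aborted patient was left out: it lists P03 to P12 without stating a selection rule, and whether any attempt was aborted cannot be known.

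**Conclusion.** The concern holds as a conflict with a biased possible outcome. Protocol 14.4 is categorical but rests on an undefined term. Protocol 6.3 collects the safety data of aborted patients, and the SAP's two populations do not between them clearly give a rate over all attempted insertions. An analyst who follows 14.4 together with the per-protocol primary analysis can leave aborted placements and their serious events out of the percentages that those events should determine, and both errors are favourable.

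The size is about 5 points per omitted patient with 20 attempts, about 8 with 12, and about 9 in the example of 10 stimulated plus 1 aborted. The counts of aborted patients are assumptions, as are the success of every other placement and a serious event in each aborted case. The documents establish that the denominator is open, not that anyone was dropped.

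**What to change.** 1. **Protocol 14.4:** limit the exclusion to subjects in whom no lead insertion was started, which also settles what counts as treated for this purpose.
2. **Both safety percentages, protocol and SAP:** state that the denominator is all patients with any insertion attempt. Score an aborted attempt as unsuccessful placement and count its adverse events.
3. **SAP section 2:** restate the intent-to-treat population as all patients in whom insertion was attempted, including those aborted.
4. **Protocol 11.6.2:** limit it to decisions made before insertion starts, and reconcile it with enrolment at consent in 6.3.
5. **SAP Table 3:** let it list every attempted patient. As it stands it has no rows for the first two patients, whom SAP section 2 keeps for the safety analysis.

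The cost is wording in two documents. No new data are needed, because 6.3 already requires follow-up of aborted patients. The downside is that the reported percentages may look less favourable.

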14.5 Study Final Report

The final report will be compiled by Stimdia Medical, Inc. and reviewed, approved and signed off by the Principal Investigator of participating site(s).

14.6 Study Material and Data Retention/Archiving

Data files used for statistical analyses will be retained by each investigational center and study sponsor for at least 10 years after the study has been completed.

15. TRAINING AND EXPERIENCE REQUIREMENTS

Sponsor will maintain records documenting all training.

15.1 Clinical Investigation Plan (CIP) Training

Prior to subject enrollment, Sponsor/CRO will conduct training that will include reviewing the CIP, study procedures and study administrative procedures. Sponsor or designee will provide periodic updates to review procedures changes, amendments to the CIP, or for any changes in investigative team members at the site.

15.2 Device and Procedure Training

To ensure familiarity with the instrumentation and treatment techniques, Sponsor will train each Investigator prior to enrolling their first subject in the clinical investigation and may attend some or all of the cases at each Investigation site to ensure proper device use.

16. ETHICAL, REGULATORY AND ADMINISTRATIVE REQUIREMENTS

16.1 Ethics Committee and Regulatory Approvals

Before study commencement, the Principal Investigator must submit the Clinical Investigation Plan, Investigator's Brochure, Essential Requirements Checklist, Patient information sheet and Informed consent form and any other documents as may be required to the appropriate Ethics Committee (EC) for review and approval. The Principal Investigator, and any other member of the investigative team, is a member of the Ethics Committee, must not participate in the decision-making. A signed and dated EC approval letter must be provided to Sponsor. The study will not start until written documentation of all required local and national regulatory approvals are obtained.

Any report of withdrawal of Ethics Committee approval will be submitted to the Sponsor within five (5) working days.

16.2 Informed Consent and Patient Information

A signed and dated informed consent must be obtained for all subjects enrolled. The Principal Investigator must explain to each subject or his/her legally authorized representative the nature of the clinical investigation, including any risks and benefits, its purpose and procedures, and expected duration of involvement in the clinical investigation. The subject or his/her legally authorized representative must have the opportunity to ask questions and must be informed that participation in the clinical investigation is voluntary and non-participation will not affect his / her right to the most appropriate standard treatment or affect the doctor/clinician-patient relationship. Subjects or their legally authorized representatives have full rights to withdraw from the clinical investigation at any time, irrespective of their initial consent.

Each subject must also give their permission for representatives of the Sponsor, auditor and regulatory authorities to review their hospital records for the purposes of source data verification. The informed consent form must also be signed and dated by the research team member obtaining consent. The signed informed consent form must remain in the subject's study file and be available for review by the study monitor.

16.3 Protocol Deviations

A protocol deviation is defined as an event where the clinical Investigator or site personnel did not conduct the study according to the Investigational Plan or the Investigator Agreement. The Investigator is not allowed to deviate from the Investigational Plan.

Under emergency circumstances, deviations from the protocol to protect the rights, safety and well-being of human subjects may proceed without prior approval of the sponsor and the Ethics Committee. Reports of any deviation from the protocol under emergency circumstances will be reported to the Sponsor and to the Ethics Committee as soon as possible after detection, but no later 5 working days from the time of the deviation.

Deviations shall be reported to the study sponsor regardless of whether medically justifiable, preapproved, or taken to protect the subject in an emergency. Subject specific deviations will be reported on the Case Report Form or Protocol Deviation Form. Non-subject specific deviations will be reported to the Sponsor in writing. Investigators will also adhere to procedures for reporting study deviations to their EC in accordance with their specific EC reporting policies and procedures.

Any deviations from the protocol must be documented in detail by the Investigator and reported to the study monitor as soon as possible.

Regulations (ICH-GCP/EN ISO 14155) require that Investigators maintain accurate, complete and current records, including documents showing the dates and reasons for each deviation from the protocol.

The following deviations are considered as major:

- ICF collection process not respected.
- Inclusion/Exclusion criteria not respected.

- Misuse of medical device.
- Lack in SAE reporting.
- Any protocol assessment in relation with the primary endpoints that is not respected.

If a Study Monitor becomes aware that an Investigator is not complying with the signed Investigator's Agreement, the Investigational Plan, the requirements of ICH-GCP/EN ISO 14155 or other applicable regulations, or any conditions of approval imposed by the reviewing Ethics Committee, Sponsor will immediately either secure compliance or discontinue shipments of the device to the Investigator and terminate the Investigator's participation in the investigation. The Investigator will be required to return all investigational devices, unless this action would jeopardize the rights, safety or welfare of a patient.

Protocol deviations will be analyzed by Sponsor for the impact to the overall integrity of the study. Disqualification is warranted when an investigator has repeatedly or deliberately violated governing regulations or has repeatedly or deliberately submitted false information in any report. Where protocol deviations occur which do not warrant disqualification from a study, Sponsor will implement appropriate corrective and preventive actions, including repeat training as deemed necessary.

16.4 Amendments

The Clinical Investigational Plan, CRFs, Informed consent form and other subject information, or other clinical investigation documents will be amended as needed throughout the clinical investigation, and a justification statement will be included with each amended section of a document. Proposed amendments to the Protocol will be agreed upon between the sponsor and principal investigator(s).

The amendments to the Protocol and the subject's informed consent form will be submitted to obtain approval the EC and regulatory authorities, if required. The version number and date of amendments will be documented.

16.5 Investigational Device Accountability and Storage

The investigator must ensure that the device is used only in accordance with the protocol. Each individual PEPNS System that is used will be fully traced in the subjects' medical records and the Clinical Investigator File to ensure full accountability.

The investigator or designee is responsible for device accountability at the trial site i.e., to keep records documenting the receipt, use, return and disposal of the investigational devices. For that, a Device Accountability Log (DAL) will be provided to each investigational site. Such log shall record dates, quantities, batch/serial numbers, expiration dates, and the unique code numbers assigned to the trial subjects, and date of procedure. A space will be provided for recording returned product and the reason for the return. The investigator should maintain records that adequately document that subjects were treated with the investigational device as specified by the protocol.

Upon receipt of an investigational device shipment, the Investigator or designee is required to reconcile inventory of the product received and verify the shipment by signing the packing list. All investigational devices must be stored in a locked storage facility to which only the investigator or designee will have access. The secure location should be a dry and ambient room temperature location.

16.6 Monitoring Plan

The study monitor will be responsible for securing the compliance of Principal Investigator(s) to the signed clinical trial agreement.

The study monitor appointed by the sponsor to oversee the conduct and progress of the study is the primary communication link between the sponsor and Investigator. Monitor responsibilities may include investigator selection and training, assurance of current Ethics Committee approvals, periodic on-site inspection and audit of site records to ensure continued compliance with the protocol, adequacy of the investigator and the facility to carry out the study, and verification that the device is being used in accordance with instructions for use.

Functions that the monitor/sponsor will perform include:

- Pre-Investigation Screening to ensure sufficient staffing, cooperation, investigator training and adequate numbers of potential subjects.
- Review of study required documentation including signed agreements, protocol, required institutional approvals, Ethics Committee Approval.
- Study site initiation to review with site staff the protocol requirements, case report forms, data collection methods and any electronic data capturing system. Requirements for timely and accurate reporting of clinical data and unanticipated adverse events will be reviewed. During this visit the monitor will ensure training in proper use of the investigational device as well as ensuring safe and secure storage of study devices and device accountability.
- Investigational device accountability records will be reviewed including devices received, receipt dates, quantity, lot numbers, storage and signature of study personnel responsible for accountability.
- Personal contact with the investigator and staff throughout the study by telephone, mail and on-site visits, to continue until study is completed. This monitoring will ensure continued protocol compliance, adequate enrollment, accurate data reporting and query resolution and continued Ethics Committee approval of the study. A full record of monitoring activities will be maintained.
- Final on-site study close out visit at the completion of the investigation to collect outstanding documents and resolve outstanding queries, confirm site files are complete and accurate, review record retention requirements with the investigator and provide for return of unused study devices to sponsor.

